Baseline data collection. Baseline data collection (using Qualitrics) will occur before the start of the educational session, described below. Subjects with blood pressure value less than 120/80 mm Hg during this visit (second blood pressure reading) will no longer qualify for this study. The gold standard BP measurement using a sphygmomanometer through auscultation will be taken twice, five minutes apart to be averaged. Other baseline data include: anthropometry (height and weight), Automated Self-Administered 24-Hour Dietary Assessment Tool (ASA24) focusing on sodium intake, pre-test Hypertension Knowledge-Level Scale (HK-LS), and initial motivational level assess (using Qualitrics) using the study's iPads. We have two research iPads that are only designated for this project. The subjects will not use their own devices and the link are not send to subjects. It is already set up to collect data from the subjects. We locked the screen on the iPads so only the questionnaires can be accessed.

Aim 2 Educational session, all subjects. The PI or RA will provide a brief one-on-one or group educational talk (no more than 2 subjects, to separate intervention and control group subjects) before the 4-week trial on the importance of SMBP, elevated BP regarding CVD risk, the role of motivation in adopting lifestyle behavior, and specific behaviors to reduce BP. This is akin to HTN risk reduction advice received in an office visit.

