MOBILE Intervention in College Students with Elevated Blood Pressure

Version Date: 05/19/2021

Statistical Analysis Plan

Statistical Design and Power

Sample size. We will recruit 32 subjects to be randomized to an intervention and control arm with a ratio of 1:1 ($n = 16$ per study group), using a random number generator. A sample size comparable to a prior study of cellular phone and internet-based intervention on BP reduction that showed medium to high effect sizes (ES $f = 0.395$) on BP reduction.⁴⁹ Using an estimated ES of $f = 0.39$ for the within-subject effect (Time), we conducted a power analysis for a mixed design ANCOVA with 2 groups, 2 measurements per subject, and $r = .5$ for the bivariate correlation between two measures tested at $\alpha = 0.05$. To achieve 70% power for the significance test of the within-between interaction effect, a sample of $N = 28$ will be needed. Anticipating a 7-11% attrition rate⁴⁹ based on the previous study,⁴⁹ an initial $N = 32$ will be needed to achieve 70% power to test preliminary impact. We acknowledge that the low power level is a limitation in our pilot study; therefore, we will attempt to recruit more within the timeframe to reach a higher power level.

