Data Analysis. Aim 2: We will perform preliminary descriptive analyses on all variables, use Pearson's correlation (r) to assess relationships between primary and secondary outcome variables at each data collection point, and calculate Pearson's r to assess the stability of each outcome variable pre- and post-intervention. To evaluate feasibility and acceptability, we will use content analytic methods to identify students' likes and dislikes and suggestions for future app improvement.⁶⁵ Thematic analysis of interviews will be conducted to describe the elements of feasibility and acceptability as perceived by subjects. Participation rate will be calculated as the percentage of students enrolled out of all eligible students who are invited to participate in the study; engagement will be calculated as a percentage of students' available data out of all the intended data points. **Exploratory Aim.** "The intervention group will have a significantly greater reduction in BP and sodium intake and greater increase in HTN knowledge from baseline to completion, compared to control group." A 2x2x2 mixed design ANCOVA will be performed for each of the above primary and secondary outcomes, with Study Group (Intervention vs. Control) as the between-subject factors, years of age as the covariate. A Time effect on an outcome variable would indicate the impact of the **MOBILE** intervention on the outcome measure in college students with elevated BP.

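### The planned mixed design ANCOVA, in its classical form, compares completers without baseline adjustment, so loss that depends on baseline differently in the two arms would bias Group x Time; two standard models remove this at no cost in precision

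*SAP*

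**What the plan says.** SAP, Data Analysis (Exploratory Aim): a "mixed design ANCOVA will be performed for each of the above primary and secondary outcomes". Study group is the between-subject factor, with "years of age as the covariate"; no other covariate is named. The hypothesis concerns change: a "significantly greater reduction in BP and sodium intake and greater increase in HTN knowledge from baseline to completion, compared to control group".

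SAP, Statistical Design and Power: the design has "2 groups, 2 measurements per subject", and the powered test is the group-by-time term ("To achieve 70% power for the significance test of the within-between interaction effect"). Loss to follow-up appears once ("Anticipating a 7-11% attrition rate"), as the reason for enrolling 32 so that 28 remain.

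Neither document names an analysis set, a missing-outcome method or a sensitivity analysis. The Data Analysis section refers to available data only to define the engagement percentage.

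**The concern.** With one baseline and one week-4 value, Group x Time is the between-arm difference in mean change. The classical repeated-measures calculation needs both values, so anyone without a week-4 visit leaves the comparison, baseline included. Those who remain are no longer the randomised arms.

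Because baseline is not a covariate, nothing corrects for regression to the mean if the completers in one arm start from a different mean. Age repairs this only as far as it carries the same information.

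The arms are also followed differently. MOBILE subjects have daily readings, motivation ratings and replies, plus reminders and staff contacts (Protocol, Aim 2 MOBILE Intervention Group). Controls have one meeting four weeks later (Protocol, Aim 2 Control Group). Loss could therefore follow a different pattern in each arm. What is at stake is the direction and size of the pilot's estimate of effect on BP, sodium intake and knowledge.

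**Working it through.** **The plan's own attrition step.** 28/(1 - 0.11) = 31.5, rounded up to 32; 28/(1 - 0.07) = 30.1, rounded up to 31. From 32 enrolled, 32 x 0.89 = 28.5 to 32 x 0.93 = 29.8 remain, so 2 to 4 subjects are lost. This step reproduces, and it covers the loss of precision. (Separately, 70% power at N = 28 does not follow from f = 0.39 and r = .5: the noncentrality f² x N x 2/(1 - r) = 0.39² x 28 x 2/0.5 = 17.0 gives 97.8%. That does not affect the present point.)

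**Bias formula.** Let b be the slope of the week-4 value on baseline, the same in both arms. If completers' mean baseline differs from the randomised mean by s_M in MOBILE and s_C in control, and loss depends only on baseline, the week-4 means move by b x s_M and b x s_C. The error in the difference in change is then

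bias = -(1 - b)(s_M - s_C).

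It is zero if loss is unrelated to baseline, if the shifts are equal in the two arms, or if b = 1.

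**Inputs.** From the SAP: 16 per arm, r = .5, overall loss 7-11%. Assumed, because the documents do not give them: SD 10 mmHg at both times (so b = r), normally distributed baseline, true effect 0, logistic loss rising with baseline in MOBILE only, and the loss rates by arm. The odds of loss rise by a factor of 2.7 per SD in the first two scenarios and 4.5 in the third. The logistic intercept is set so that total MOBILE loss equals the stated rate. r = .3 is added as a sensitivity value.

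| MOBILE/control loss | s_M | Bias, r = .5 | Bias, r = .3 |
|---|---|---|---|
| 11%/11% | -0.099 SD | 0.5 x 0.99 = 0.50 mmHg | 0.7 x 0.99 = 0.69 mmHg |
| 15%/5% | -0.133 SD | 0.5 x 1.33 = 0.66 mmHg | 0.7 x 1.33 = 0.93 mmHg |
| 20%/5% | -0.227 SD | 0.5 x 2.27 = 1.13 mmHg | 0.7 x 2.27 = 1.59 mmHg |

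The sign is positive for change: losing high baselines from MOBILE makes its reduction look smaller. Losing low baselines would do the opposite. The third scenario averages (20 + 5)/2 = 12.5%, slightly above the plan's range.

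**Simulation** (20,000 trials per scenario, r = .5; change-score analysis of completers):

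| Loss | Bias | SE | Type I error |
|---|---|---|---|
| 11%/11% | 0.48 | 3.74 | 5.0% |
| 15%/5% | 0.67 | 3.72 | 5.4% |
| 20%/5% | 1.11 | 3.78 | 6.0% |

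The SE agrees with the formula: the SD of change is 10 x √(2 x 0.5) = 10, and 10 x √(2/14.24) = 3.75 with 16 x 0.89 = 14.24 per arm. The bias is 0.50/3.74 = 0.13 to 1.13/3.78 = 0.30 of an SE.

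**Same data, alternative analyses.** An estimate that uses every randomised baseline (a regression form that approximates the likelihood model) has bias within 0.05 mmHg and SE 3.7-3.8. ANCOVA of the week-4 value adjusted for baseline, on the same completers, has bias within 0.03 mmHg and SE 3.3-3.4.

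**Two limits.** With the same baseline-related loss in both arms (11%/11%), the change-score bias is 0.00. As a ceiling, suppose the full 11% of 32 falls in one arm (22% of that arm) and removes exactly its highest baselines. The shift is then 0.38 SD and the bias 0.5 x 3.8 = 1.9 mmHg, about half an SE.

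**The case against.** The case for leaving the plan as it is has real weight. The aim is exploratory, in a pilot that admits low power and whose key Aim 2 outcome is acceptability. Two to four people are expected to be lost, precision is already covered, and the bias is under a third of an SE at r = .5 in the three scenarios. All of this stands and limits how much the point matters. It does not favour the planned analysis, because the alternatives cost no precision.

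A reader might draw stronger conclusions that the documents do not support:

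- **That the SAP prescribes a completer analysis.** It does not say so. This is inferred from the classical form of the named method and from the way attrition is handled.
- **That dropping subjects is by itself the cause.** The bias needs both the shifted completers and the missing baseline adjustment; adjusting for baseline on the same completers removes it.
- **That any baseline-related loss biases the result.** Equal dependence in both arms cancels.
- **That MOBILE will lose more subjects.** Its burden is heavier, but its procedures also include a 72-hour follow-up, reminder messages, two staff contacts, a meeting invitation after silence and return of the cuff. No control contact is described between baseline and week 4. No per-arm rate is given, and loss could be higher in either arm.
- **That the rule on devices ("The subjects will not use their own devices and the link are not send to subjects") makes one missed week-4 visit cost the questionnaires too, so they should be completed remotely.** That sentence is under Baseline data collection. The follow-up text mentions a meeting and Qualtrics, not iPads. Unsupervised knowledge tests, used more in the arm with more loss, could bias that comparison, so no such change is proposed.

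**Conclusion.** The point holds as a modest, conditional risk of bias with a free remedy. The SAP expects loss, does not say how lost subjects are analysed, and names a method that in its usual form compares completers' changes without baseline adjustment. If loss depends on baseline differently by arm, the bias is about 0.5, 0.6-0.7 and 1.1 mmHg in the three scenarios at r = .5, against an SE of 3.7-3.8. At r = .3 it is about 0.7, 0.9 and 1.6 mmHg.

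These figures rest on an assumed SD of 10 mmHg and scale with it. They also rest on equal SDs at both times, a normal baseline (an approximation, since entry excludes readings below 120/80) and loss related to baseline in MOBILE only. Under that pattern the benefit of MOBILE would be understated. The documents do not establish that such loss will occur.

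**What to change.** In SAP, Data Analysis (Exploratory Aim), state that every randomised subject is analysed in the assigned arm, and choose one of two models for each outcome:

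1. A likelihood-based (REML) linear mixed model with Group, Time and Group x Time, an unstructured 2x2 covariance, age kept as covariate and small-sample degrees of freedom. Subjects with baseline only are included.
2. ANCOVA of the week-4 value adjusted for baseline and age. It uses subjects with a week-4 value, also removes this bias, and has the smaller SE (about 3.3-3.4 against 3.7-3.8 mmHg at r = .5). The SAP should then say that subjects without a week-4 value do not contribute.

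In either case, report loss by arm against the 7-11% assumption, and state that neither model corrects loss that depends on unobserved outcomes.

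The cost is a few sentences in the SAP and a different standard procedure. No extra subjects, visits or data are needed.

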If we haven't heard from the subject for more than 7 days, we will invite the subject to a meeting to explore why the subject hasn't been participating. Such meetings will give us an opportunity to identify barriers and challenges subjects are experiencing and to remind them why they enrolled in the first place. An RA will contact each subject two times during the 4-week intervention to (a)

explore the acceptability of and engagement with the intervention and (b) reinforce study participation. Subjects can always withdraw from the study if they wish to do so.

Aim 2 Control Group. Following the educational session, the control group subjects' BP, ASA24 (sodium intake), and pre-test knowledge on HTN will be obtained (using Qualtrics). Four weeks later, the subject will be scheduled for a follow-up meeting to collect each subject's BP, ASA24, and post-test knowledge on HTN (using Qualtrics).

Aim 2 Post-intervention data collection and intervention engagement. We will schedule a post-intervention meeting with each subject for data collection (gold standard BP) and return of the Withings BP cuff (intervention group only). We operationalize acceptability, the key Aim 2 outcome, as the subject's favorable perception of the **MOBILE** intervention as being appropriate and reasonable in addressing their elevated BP, convenient to use, easy to apply to their daily lives, and effective in addressing their elevated BP both currently and long-term. Data on acceptability and other study variables will be gathered using questionnaires and open-ended questions in a semi-structured exit interview (using Qualtrics). The research team will monitor the intervention for subject acceptability operationalized as active and continual participation in the intervention (receiving the subject's daily BP value), and favorable responses to the tailored change behavior SMS. The team will also measure engagement with the intervention, operationalized as the extent to which the subject followed the self-monitoring protocol. The self-report survey and semi-structured interview script will be created and implemented by the research team during the formative phase. The intervention subjects will be informed that they may delete the Health Mate app at any time once their participation is completed. The research team will no longer have access to their BP data once they completed the study.

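### Impact is read from a Time effect and only age is adjusted for; a between-arm ANCOVA on each outcome's own baseline would match the hypothesis and may be more precise for sodium and HK-LS

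*SAP*

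**What the plan says.** The hypothesis in the SAP (Data Analysis, Exploratory Aim) is between arms: BP and sodium intake should fall more, and hypertension knowledge rise more, with the intervention than with control. The model is introduced as follows: "A 2x2x2 mixed design ANCOVA will be performed for each of the above primary and secondary outcomes". Only one factor and one covariate are then listed for it: "with Study Group (Intervention vs. Control) as the between-subject factors, years of age as the covariate". No outcome's baseline is listed as a covariate. The paragraph ends by naming the effect that is to count as evidence for the app: "A Time effect on an outcome variable would indicate the impact of the".

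The SAP's Sample size section powers a different effect, the "significance test of the within-between interaction effect", for two arms measured twice, with 70% power at N = 28. It uses a single planning correlation of .5, described as being "for the bivariate correlation between two measures tested at"; the significance level is 0.05.

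Four places in the Protocol bear on this:

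- **Baseline data collection** lists BP, ASA24 sodium and HK-LS as baseline measures, and selects on BP: "Subjects with blood pressure value less than 120/80 mm Hg during this visit (second blood pressure reading) will no longer qualify".
- The education talk goes to both arms, under the label "Aim 2 Educational session, all subjects".
- **Post-intervention data collection** says "We operationalize acceptability, the key Aim 2 outcome", so the comparison at issue here is exploratory.
- **Baseline timing** is given in two ways. Baseline data collection puts it ahead of the educational session. Aim 2 Control Group has the control subjects' BP, ASA24 and knowledge pre-test obtained after that session.

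**The concern.** The effect named as evidence of impact does not compare the arms. A Time main effect is the average change over intervention and control together. Both arms are educated, so both could improve with no contribution from the app, and the Time effect would still appear.

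The interaction in the power section does compare the arms. With only two time points it is the group comparison of follow-up minus baseline, so baseline enters with its slope fixed at 1 instead of estimated. With 14 to 16 subjects per arm, the resulting loss of precision is worth avoiding, because the baseline values are collected anyway.

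The model also cannot be fitted exactly as written. Study Group is named and Time is implied, but the third two-level factor of the 2x2x2 design is not identified.

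**Working it through.** **1. The plan's own figure.** By the usual noncentral F convention for the interaction, lambda = f² x N x m/(1 - r) = 0.39² x 28 x 2/0.5 = 17.0 on 1 and 26 df. This gives 97.8% power at N = 28, and 70% is reached at N = 14. The stated N = 28 does not reproduce (the attrition step does: 28/0.89 = 31.5, rounded up to 32). That is a separate matter. Its bearing here is that there is no sound base from which to claim a power gain, so only precision is compared below.

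**2. What a Time test would show.** Assume r = .5, N = 28, no covariate, and an equal 0.5 SD improvement in both arms. The SD of change is sqrt(2(1 - .5)) = 1 SD, its mean has SE 1/sqrt(28) = 0.189, and 0.5/0.189 = 2.65. Time is then significant in about 72% of trials with no intervention effect.

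**3. Change score against baseline ANCOVA, equal SDs (sodium, HK-LS).** Var(change) = 2(1 - r)SD². The residual variance after baseline adjustment is (1 - r²)SD². The ratio is (1 + r)/2. At N = 28, with age in both models, ANCOVA has 24 df instead of 25 (t = 2.064 against 2.060), and one more slope inflates the variance by about 1 + 1/23. The cost in CI width is sqrt(1 + 1/23) x 2.064/2.060 = 1.0235. The last column is a simulation of 20,000 trials per setting, with age unrelated to the outcome.

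| r | variance ratio | CI width ratio, sqrt(ratio) x 1.0235 | simulated |
|---|---|---|---|
| .3 | 0.65 | 0.825 | 0.825 |
| .5 | 0.75 | 0.886 | 0.886 |
| .7 | 0.85 | 0.944 | 0.943 |
| .9 | 0.95 | 0.998 | 0.997 |

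At 16 per arm and r = .5 the simulated ratio is 0.884.

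**4. Unequal SDs.** With s = baseline SD/follow-up SD, the variance ratio is (1 - r²)/(1 + s² - 2rs). At r = .5:

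- s = 0.8: 0.75/0.84 = 0.893, CI ratio 0.967.
- s = 0.5, that is s = r: 0.75/0.75 = 1, CI ratio 1.023. The true slope is then 1 and only the cost remains.

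**5. BP.** Assume selection directly on baseline at -1, 0 or +0.5 SD, with equal SDs and correlation r before selection, so that the slope b = r. The retained baseline SDs are 0.794, 0.603 and 0.518, so the retained variance v is 0.630, 0.364 and 0.268. The variance ratio is (1 - b²)/[(1 - b²) + (1 - b)²v]. At b = .5 this is 0.75/0.9075 = 0.826, 0.75/0.841 = 0.892 and 0.75/0.817 = 0.918. Simulated CI width ratios at 14 per arm:

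| r before selection | cut-off -1 SD | 0 | +0.5 SD |
|---|---|---|---|
| .5 | 0.929 | 0.966 | 0.980 |
| .7 | 0.970 | 0.992 | 0.999 |
| .8 | 0.989 | 1.002 | 1.008 |
| .9 | 1.007 | 1.013 | 1.016 |

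If .5 is instead the correlation among enrolled subjects, the ratios are 0.948, 0.990 and 1.004. In all settings of steps 3 to 5, both methods rejected a true null in 4.5% to 5.4% of trials.

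**6. Chance imbalance.** At 14 per arm a 1-SE baseline gap is sqrt(2/14) = 0.378 SD. At r = .5 it moves the change-score estimate by (1 - .5) x 0.378 = 0.189 SD and leaves the adjusted estimate where it is. But 0.189²/(2/14) = 0.0357/0.1429 = 0.25, which is the 25% of step 3 seen conditionally.

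**7. Baseline timing.** Suppose the control baseline alone is shifted by 0.5 SD, with slope .5 and no true effect. The change score shows 1 x 0.5 = 0.50 SD, and ANCOVA shows 0.5 x 0.5 = 0.25 SD. Both are biased, by different amounts.

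**The case against.** The strongest objection is that the precision argument concerns a test the analysis paragraph never names. Group x Time appears only in the power section, and the analysis paragraph names Time. On that view the real error is reading Time as impact, and the missing baseline covariate is a choice between two valid estimators. This stands as a matter of weight. The Time reading is the more serious part, and the baseline covariate is an efficiency improvement that the same rewording can deliver.

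The gain is also modest. At 14 per arm and r = .5 the half-width goes from about 2.060 x 0.378 = 0.78 SD to 0.78 x 0.886 = 0.69 SD. Neither interval supports an efficacy conclusion, and the SAP already concedes low power. This stands too.

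The inputs are thin. The plan gives r once, in a calculation built on a BP effect size, and gives no correlation or SD for sodium or HK-LS. The BP cut-offs are assumed, whereas the Protocol screens on the second reading with a joint systolic and diastolic limit and averages two readings for baseline. The omission is certain; its size is conditional.

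A reader might draw three stronger conclusions, none of which the documents support:

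- *That the age-only interaction test is biased or invalid.* Allocation is random, so the change-score test is valid if baselines are taken comparably in both arms.
- *That chance imbalance is a second loss on top of the lost precision.* Step 6 shows that it is the same loss.
- *That adjustment would lift power from 70% to a stated higher figure.* The plan's own inputs do not give 70% at N = 28.

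**Conclusion.** The point holds as a low-cost improvement to an exploratory pilot analysis. The Time effect does not address the stated hypothesis, and this conclusion needs no assumption. The change-score test behind the power statement does address it, at some cost in precision.

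- **Sodium and HK-LS**, if r = .5 applies and SDs are equal: 25% less residual variance and a CI about 11% narrower at 14 per arm. Over r from .3 to .9 the gain runs from 18% to under 1%. At r = .5 it falls to 3% with an SD ratio of 0.8, and becomes a CI about 2% wider if that ratio equals r.
- **BP**: from about 7% narrower to 2% wider under the assumed cut-offs, so possibly no gain.

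All of this presumes that baseline is measured at the same point in both arms, which the Protocol leaves contradictory. Confidence is high that the covariate is omitted and that Time is the wrong contrast, and lower on the size of the gain.

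**What to change.** **First, as a precondition:** reconcile the Protocol's Baseline data collection and Aim 2 Control Group sections on whether baseline comes before or after the educational session, identically in both arms. Otherwise a baseline covariate could itself differ between arms by design.

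**Then, in the SAP's Exploratory Aim:**

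- For each outcome, prespecify an ANCOVA of the 4-week value on Study Group, that outcome's own baseline, and age.
- Report the adjusted between-arm difference with its 95% CI as the intervention effect, in place of the Time effect.
- Keep Group x Time only as a sensitivity analysis.
- Name the third factor of the 2x2x2 model or drop it. If it is a between-subject factor, add it as a term; if it indexes two measures, fit one ANCOVA per measure, each with its own baseline.

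**Cost:** SAP wording and no new measurements, plus the timing clarification in the Protocol. Statistically, one degree of freedom (24 instead of 25 at N = 28, or 23 if a between-subject third factor is kept). BP may gain nothing, or have a CI up to about 2% wider, if r is high; the same applies to any outcome whose baseline/follow-up SD ratio is close to r.

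### The SAP credits MOBILE with a Time effect, which averages change over both arms; the stated hypothesis is answered by Group × Time

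*SAP*

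**What the plan says.** The SAP (Data Analysis, Exploratory Aim) states a between-arm hypothesis: "The intervention group will have a significantly greater reduction in BP and sodium intake", together with a greater gain in hypertension knowledge, relative to control. The model is given as follows: "A 2x2x2 mixed design ANCOVA will be performed for each of the above primary and secondary outcomes", with study group "as the between-subject factors, years of age as the covariate". The paragraph ends with its rule for reading the results: "A Time effect on an outcome variable would indicate the impact of the" MOBILE intervention. It never mentions the Group × Time interaction.

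The SAP's Sample size section rests on a different term: "To achieve 70% power for the significance test of the within-between interaction effect", it calls for 28 subjects. The effect size of f = 0.39 that goes into that calculation is, however, assigned to the within-subject Time effect.

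Three features of the protocol bear on how far both arms may change without MOBILE:

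- The educational session is given to all subjects (Aim 2 Educational session).
- Entry depends on a baseline reading: "Subjects with blood pressure value less than 120/80 mm Hg during this visit (second blood pressure reading) will no longer qualify for this study". The two baseline readings are then averaged (Baseline data collection).
- Timing is stated in two ways. Baseline data collection "will occur before the start of the educational session, described below", but under Aim 2 Control Group, "Following the educational session, the control group subjects' BP, ASA24 (sodium intake), and pre-test knowledge on HTN will be obtained".

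**The concern.** The hypothesis asks whether the arms differ in their change. The reading rule asks whether subjects changed on average, whichever arm they were in. These are different questions and can have opposite answers. If both arms improve equally, Time is significant although MOBILE did nothing. If the arms move in opposite directions, Time can be null although they differ.

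Shared change is plausible in this design. Subjects are selected on a raised blood pressure reading, so some fall at four weeks through regression to the mean is to be expected in both arms. Both arms also receive the educational session, and any effect of it that follows baseline is part of Time. The written rule would credit all of this to MOBILE, for blood pressure, sodium and knowledge alike.

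Acceptability is the key Aim 2 outcome, so this does not undermine the pilot as a whole. What is at stake is the preliminary efficacy signal, which is what a later trial would be built on.

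**Working it through.** **1. The plan's own figure.** Inputs from the SAP's Sample size section: f = 0.39, r = .5, 2 groups, 2 measurements, α = 0.05, N = 28 for 70% power. The usual noncentrality for a within-between interaction is λ = f²·N·m/(1 − r) = 0.39² × 28 × 2/0.5 = 17.0. On 1 and 26 df this gives 98% power, and 13 subjects (14 with equal arms) would give 70%. N = 28 is therefore not reproduced by this formula, nor by the other two-sided forms tried. The attrition step does reproduce: 28/(1 − 0.11) = 31.5, rounded up to 32. This is a separate matter. The present point concerns which term is read and does not depend on N = 28 being right.

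**2. What each term measures.** Let the mean pre-post change be c in control and c + δ in intervention, with equal arms. Then:

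- Time = c + δ/2
- Group × Time = δ

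The hypothesis is about δ. With δ = 0, Time equals c, the shared change.

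**3. How often Time is significant when δ = 0.** Inputs: N = 28 or 32 and r = .5 from the SAP. The shared change d, in baseline SDs, is an assumption. The model has Group, Time and centred age only, since no third factor is identified. The SD of change is √(2(1 − r)) = 1 SD at r = .5. The Time test is F on 1 and N − 3 df with λ = N·d²/(2(1 − r)). At N = 28 and r = .5, λ = 28 × 0.2² = 1.12, 28 × 0.3² = 2.52 and 28 × 0.5² = 7.00.

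| Setting | d = 0.2 | d = 0.3 | d = 0.5 |
|---|---|---|---|
| Time, N = 28, r = .5 | 17% | 33% | 72% |
| Time, N = 32, r = .5 | 19% | 38% | 78% |
| Time, N = 28, r = .3 | 14% | 25% | 58% |
| Time, N = 28, r = .7 | 26% | 50% | 91% |
| Group × Time, all settings | 5% | 5% | 5% |

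A simulation of 20,000 trials at N = 28, r = .5 agreed: Time 16.8%, 33.8% and 72.0%; Group × Time 5.1%, 5.1% and 4.8%.

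**4. The opposite failure.** If the arms change by +0.39 and −0.39 SD (assumed), the between-arm difference is 0.78 SD. Time is then significant in about 5% of trials and Group × Time in about 51%.

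**5. Age not centred.** The SAP does not say whether age is centred. If it is uncentred and a Time × age term is fitted, Time is the change at age zero. With mean age m and SD s, λ = d²/(1/28 + m²/(27s²)). For assumed m of 20 to 27 and s of 2 to 7, the rates for d = 0.2, 0.3 and 0.5 are 5–6%, 5–8% and 5–13%. They are lower because the term is poorly estimated. It is still not an intervention effect.

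**6. Baseline timing.** Suppose controls are measured after the educational session and intervention subjects before it. An education effect d then enters only the intervention arm's change, and so enters Group × Time: λ = (N/4)·d²/(2(1 − r)) = 7d² at N = 28, r = .5, that is 0.28, 0.63 and 1.75. On 25 df, Group × Time is significant in 8%, 12% and 25% of trials with no MOBILE effect.

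**The case against.** The best defence is that the interaction was meant all along. The hypothesis is stated against control, and the Sample size section powers the interaction and ties the resulting N to testing preliminary impact. That section also attaches f to Time and then uses it for the interaction, so the authors may be using the word loosely. An analyst guided by the hypothesis would probably report Group × Time anyway. This is a fair account of the likely intention, but it does not repair the text. The same section names the within-subject Time effect and the within-between interaction as separate things, and the only reading rule names the former.

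The size is also open to challenge. The shared change is assumed, and the percentages run from about 5% to 91% depending on that change, on r and on how age enters. No single figure should be taken as the expected error rate. The error in the rule does not depend on any of them.

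Two side points need limits:

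- The reference to a second reading may mean the second of the two averaged readings, or the baseline visit as a check after screening. Regression to the mean is plausible either way, but its exact route is not established.
- Measuring controls after the session would mainly affect knowledge. A 24-hour dietary recall taken soon after a talk mostly covers intake before it, and nothing in the documents suggests that blood pressure changes at once.

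Finally, the aim is exploratory in a 32-subject pilot that admits low power. This limits the consequence but is no reason to keep the sentence.

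**Conclusion.** The concern holds. As written, the rule tests change averaged over both arms and would attribute it to MOBILE, contrary to the SAP's own hypothesis and power basis. Under the plan's N = 28 and r = .5, with centred age, a two-factor model and no MOBILE effect, an assumed shared change of 0.2 to 0.5 SD yields a false claim of impact in 17% to 72% of trials, against 5% for the interaction. The direction of the error is certain; its size rests on the assumed shared change. It should be corrected before analysis.

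The conflict over when control baseline measures are taken is also real. It matters more once Group × Time is the test, because unequal timing would bias that term. The unexplained third factor in the 2x2x2 label and the handling of age are minor, and the conclusion does not rest on them.

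**What to change.** Replace the last sentence of the SAP's Data Analysis section with: *The Group × Time interaction (the between-arm difference in change, with 95% CI, age centred at the sample mean) tests the impact of MOBILE. The Time main effect will not be interpreted as an intervention effect.*

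In the model sentence, identify the third factor in the 2x2x2 label or remove it.

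In the protocol, reconcile Baseline data collection with Aim 2 Control Group, so that baseline measures are taken at the same point relative to the educational session in both arms.

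The cost is wording only: one SAP sentence, the model label and one protocol sentence. No added subjects or measurements are needed.
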